5.1.1.1.1 Relative day

Relative day for an event will be derived with the date of the first SC infusion of IMP as reference.

Relative days for an event of measurement occurring before the date of first SC infusion will be prefixed with '-' and are calculated as follows:

Relative Day = [(Event Date – Date of First Infusion)]

Relative days for an event or measurement occurring on or after the date of first SC infusion are calculated as follows:

$$\text{Relative Day} = [(\text{Event Date} - \text{Date of First Infusion}) + 1]$$

For events or measurements occurring after the date of the last SC infusion, relative day will be prefixed with '+' in the data listings and are calculated as follows:

$$\text{Relative Day} = + [(\text{Event Date} - \text{Date of Last Infusion})]$$

There is no relative Day 0. Relative day is not calculated for partial dates in cases where relative day is shown in a participant data listing. In such cases, relative day should be presented as '---' in the participant data listings.

5.1.1.2 End date of the Treatment Period

The end date of the Treatment Period will be either the date of EOT visit (Week 25) for participants completing the Treatment Period, or the date of the early discontinuation (EDisc) visit for participants who discontinued during the Treatment Period. If a subject does not have an EOT/EDisc visit, then either the date of the last scheduled or unscheduled visit during the Treatment Period or the date of last known dose of IMP during the Treatment Period, whichever is later, will define the end date of the Treatment Period.

5.1.1.3 Study periods

The maximum study duration per study participant is 38 weeks. There are 3 study periods:

- Screening Period: up to 42 days;
- Treatment Period: 24 weeks;
- Safety Follow-Up Period: 8 weeks.

The following definitions for starting and entering the study periods will be applied:

- **Screening Period** starts at the time of the informed consent date and ends the day before the first dose administration of IMP (i.e. generally the day before Day 1 visit date).
- **Treatment Period** starts on the day of first dose administration of IMP (Day 1) and ends at EOT visit or at EDisc visit for participants withdrawn from the study before Week 24 visit. Participants who are withdrawn from the study during the Treatment Period should complete the assessments outlined for the EOT/EDisc visit and enter the SFU Period.
- **Safety Follow-Up Period** starts with one day after Treatment Period and ends at the final assessments at the EOS visit. Participants who have a completed status in the study termination CRF are considered to have completed the Treatment and SFU Period (i.e. entire study).

Notes:

- The end of the study is defined as the date of the last visit of the last participant in the study.
- Patients should be dosed within 2 days of being randomized.

5.1.1.1.4 Mapping of assessments performed at Early Discontinuation Visit

Assessments performed at EDisc Visit will be assigned to the next scheduled site visit (following the last scheduled visit that the participant completed prior to EDisc Visit) where each assessment is evaluated as per protocol. This approach means that there is a chance that EDisc Visit will be mapped to different visits according to the schedule of assessments.

5.1.1.1.5 Definition of Baseline values

Baseline will be derived in the screening period prior to randomization for efficacy assessments including RBANS, seizure counts, and on the date of randomization for PK/PD markers prior to the first dose of IMP. If there are multiple assessments, then the last one available prior to the randomization date will be used. Scheduled or unscheduled measurements can be used as the Baseline value. If a Baseline measurement is not available, but an unscheduled measurement occurs after the planned baseline measurement time point but before randomization, then the unscheduled measurement will be used.

For Modified Rankin Scale (mRS), the Baseline score will be the better (i.e., the lower) score from either the Screening or Baseline visit.

For safety assessments, a Baseline value will be the last available predose value if not otherwise stated.

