## **8.8           Pharmacodynamics**

Venous blood samples will be collected at time points specified in the Schedule of Activities (Section 1.3) for measurement of:

- Total serum IgG concentrations
- Serum IgG subclass concentrations
- Serum LGI1 autoantibody (total and subclasses) concentrations

Cerebrospinal fluid will be collected as specified in the Schedule of Activities (Section 1.3) for measurement of LGI1 autoantibody (total) concentrations. This sampling is optional for study participants and requires informed consent. A decision not to consent does not exclude the study participant from the study. Cerebrospinal fluid samples collected between onset of disease and Visit 2 are eligible to replace Visit 2 samples.

For all PD assessments, samples will be collected predose. Instructions pertaining to sample collection, processing, storage, labeling, and shipping are provided in the laboratory manual.

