### **9.2 General statistical considerations**

Summary statistics will be provided for all efficacy, safety, and Baseline or demographic variables.

Continuous variable outcomes will be summarized by visit (where applicable) with descriptive statistics represented by the number of study participants, arithmetic mean, standard deviation, median with 25th and 75th percentiles, minimum, and maximum. For the purpose of the statistical analysis or graphical presentations, some of the continuous variable outcomes may be log-transformed to accommodate the observed heterogeneity, mitigate influence of the outliers,

or fulfill the distributional assumptions required for statistical testing. Categorical variable outcomes will be summarized by visit (where applicable) using number of study participants, frequency counts, and percentages.

If not otherwise stated, a Baseline value will be the last available predose value and will be clearly defined in the study Statistical Analysis Plan (SAP). All relevant data will be listed by treatment group, visit (where applicable) and study participant.

Unless otherwise mentioned, all the statistical hypotheses will be tested at a two-sided 5% significance level.

All the analyses will be performed using SAS® version 9.3 or later (SAS Institute, NC, USA).

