6.1.7.2 Handling of repeated and unscheduled measurements

All repeated and unscheduled measurements will be presented in the listings, where applicable. The following general rules will apply to all repeated and unscheduled measurements:

- For repeated or unscheduled measurements obtained prior to the first dose of IMP the latest non-missing value (scheduled or unscheduled) will be used in the calculation of descriptive statistics (ie, Screening and/or Baseline);
- For repeated or unscheduled measurements obtained at the designated Baseline visit and prior to the first dose of IMP, the latest non-missing value (scheduled or unscheduled) will be defined as the Baseline;
- For repeated or unscheduled measurements obtained at any time point after the first dose of IMP, the scheduled values (if non-missing) will always be used in the calculation of changes from Baseline and for the descriptive statistics (ie, in summaries by time point). If repeated scheduled values are obtained at any time point, the latest non-missing will be used.

See [Section 5.6.3.1](#) for the rules applied to repeated lab results.

See [Section 5.6.3.4](#) for the rules applied to ECG triplicate measurements.

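### SAP 5.1.1.1.5 gives two incompatible Baseline rules for PK/PD markers; its tie-break, read literally, picks the Screening total IgG over the Day 1 predose value

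*SAP*

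**What the plan says.** SAP 5.1.1.1.5 (Definition of Baseline values) derives the Baseline for efficacy assessments in Screening and for PK/PD markers "on the date of randomization for PK/PD markers prior to the first dose of IMP". The next sentence carries no restriction to efficacy: "If there are multiple assessments, then the last one available prior to the randomization date will be used". The same section ends with a different rule for safety: "For safety assessments, a Baseline value will be the last available predose value if not otherwise stated".

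Three other places bear on the point:

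- Protocol 9.2 sets a default, unless stated otherwise: "a Baseline value will be the last available predose value". It leaves the clear definition to the SAP.
- SAP 6.1.7.2 says that, for repeated or unscheduled measurements at the Baseline visit before dosing, "the latest non-missing value (scheduled or unscheduled) will be defined as the Baseline".
- The notes to SAP 5.1.1.3 (Study periods) allow a gap before treatment: "Patients should be dosed within 2 days of being randomized".

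SAP 6.7 declares no changes to the analyses planned in the protocol.

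**The concern.** A Baseline rule should identify one value per participant without judgment by the programmer. This one names the randomization date in one sentence and excludes that date in the next. For total IgG the two sentences point to different samples.

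The choice matters if IgG changes between Screening and Day 1. Protocol 4.1 allows high-dose corticosteroids to start within 42 days before randomization. Protocol Table 6-2 bars immunoglobulin and plasma exchange only in the 4 weeks before Baseline. With Screening of up to 42 days, any of these could fall between the two samples. A change over that interval would then enter the reported IgG reduction as though it had occurred on treatment.

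The outputs exposed are the Baseline total IgG summary (SAP 6.1.1.2) and, in SAP 5.7.1.2.1, the change, percentage change and maximum decrease in total IgG and the geometric mean plot that overlays total IgG and its subclasses.

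**Working it through.** **Step 1. Which samples exist before treatment.** In Protocol Table 1-1, total IgG is marked at Screening and at Baseline (Visit 2). Exclusion criterion 30a also needs the Screening value. Two scheduled pre-treatment values are therefore planned for each participant. IgG subclasses and serum LGI1 IgG are first scheduled at Baseline.

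**Step 2. Apply each sentence to total IgG.**

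| Situation | Sentence 1 (on the randomization date, predose) | Sentence 2 (last value before that date) |
|---|---|---|
| Predose sample on the randomization date | Visit 2 value | Screening value |
| Predose sample 1 or 2 days after randomization | No qualifying value | Screening value; the predose sample is not eligible |

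In the usual case the sentences disagree. If the predose sample is drawn on a later dosing day, neither captures it. For subclasses and serum LGI1 IgG there is no earlier scheduled value for the tie-break to select.

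**Step 3. Does another rule settle it?** SAP 6.1.7.2 points to the latest predose value but is written for repeated or unscheduled measurements. One scheduled Screening sample and one scheduled Visit 2 sample are not clearly either. Protocol 9.2 gives way where something else is stated. The safety rule in 5.1.1.1.5 covers safety assessments only.

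**Step 4. Possible size.** The documents contain no figure to reproduce here. Let r be Day 1 IgG divided by Screening IgG, and d the true reduction from Day 1. The on-treatment value is (1 − d) × r × Screening, so

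reduction reported from Screening = 1 − (1 − d) × r.

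The documents give no r; the range 0.8 to 1.2 is assumed. The value d = 70% is borrowed from the dose rationale in Protocol 4.3, and d = 0 represents a placebo participant with no change. With the same r in both arms, the arm difference is (1 − 0.3r) − (1 − r) = 0.7r.

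| r (assumed) | Reported when d = 70% | Reported when d = 0 | Arm difference, percentage points |
|---|---|---|---|
| 0.8 | 1 − 0.3 × 0.8 = 76% | 20% | 56 |
| 0.9 | 1 − 0.3 × 0.9 = 73% | 10% | 63 |
| 1.0 | 70% | 0% | 70 |
| 1.1 | 1 − 0.3 × 1.1 = 67% | −10% (a rise) | 77 |
| 1.2 | 1 − 0.3 × 1.2 = 64% | −20% (a rise) | 84 |

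With the last predose value as Baseline, the first two result columns read 70% and 0% whatever r is.

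**Step 5. Comparability within one plot.** If the tie-break is programmed, total IgG starts from Screening and the subclasses from Visit 2, on the same axes.

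**The case against.** The strongest reply is that the sentence specific to PK/PD markers comes first and names the randomization date before dosing. The tie-break is generic and also serves RBANS and seizure counts. A programmer could reasonably let the specific sentence govern and use Day 1; SAP 6.1.7.2 leans the same way. This stands as far as it goes: a reader might infer that the SAP simply replaces Day 1 with Screening, and the documents do not support that. They support a contradiction whose outcome depends on programming.

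It can also be said that delayed dosing is only a tolerance, since Protocol Table 1-1 puts randomization at Visit 2 and its dosing footnote makes that the first dosing day. That is fair; nothing shows the tolerance was used. Nor does the SAP breach Protocol 9.2, which defers to it.

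A further reply is that drift before treatment would show in the placebo arm too, and that absolute IgG is listed and plotted by participant. Both are true, so a careful reader could detect the problem. But the placebo arm does not correct it: in the table above, the arm difference in percentage change moves with r.

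Finally, the worst-case interval is not general. Amendment 5 lengthened Screening from up to 14 to up to 42 days (Protocol 10.11), and SAP section 5 says participants were randomized under different versions up to Amendment 5. The documents do not say how many fall under each.

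**Conclusion.** The rule is internally contradictory and should be corrected before programming. The impact is limited: IgG is an exploratory endpoint, reported descriptively, in 12 participants. Any numerical effect depends on which sentence is programmed and on how far IgG moved between Screening and Day 1, which the documents do not quantify. The 64% to 76% range rests wholly on the assumed 20% movement either way; with stable IgG there is no shift.

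Three stronger readings are tempting and should not be drawn:

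- **That every PD marker is affected.** The Screening substitution concerns total IgG only; subclasses and serum LGI1 IgG have no scheduled Screening sample.
- **That results could land on opposite sides of a 70% target.** In Protocol 4.3 and 4.3.1, 70% supports the choice of dose. It is not a success criterion in this trial, and no decision turns on crossing it.
- **That CSF LGI1 needs a new Baseline rule.** Protocol 8.8 deliberately accepts earlier samples: "Cerebrospinal fluid samples collected between onset of disease and Visit 2 are eligible to replace Visit 2 samples". SAP 5.7.1.2.2 says the LGI1 summaries and plots will not be produced for the study report.

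**What to change.** In SAP 5.1.1.1.5, limit the existing tie-break to efficacy assessments and give PD markers their own sentence: Baseline is the last non-missing value obtained before the first dose of IMP, normally the Visit 2 predose sample.

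This removes the contradiction, covers dosing 1 or 2 days after randomization, puts total IgG and the subclasses on the same footing, and agrees with Protocol 9.2, SAP 6.1.7.2 and the safety rule in the same section. It leaves the CSF provision in Protocol 8.8 as it is. Where the Visit 2 sample is missing, the Screening value would serve as Baseline by the same rule.

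The cost is a one-sentence SAP edit and a check that the derivation follows it. No new data are needed.

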5.1.1.1.6 Calculation of Baseline Category of Seizure Count

The median category of seizure count will be calculated for each week of the screening period up to 6 weeks prior to randomization, and the average median value will be used as the Baseline category of seizure count.

5.1.1.2 Protocol Deviations

Important protocol deviations (IPDs) are deviations from the protocol which potentially could have a meaningful impact on study conduct or on the primary efficacy, key safety, or PK/PD outcomes (if applicable) for an individual study participant. The criteria for identifying important protocol deviations will be defined within the appropriate protocol-specific document. Important protocol deviations will be reviewed as part of the ongoing data cleaning process and data evaluation. All IPDs will be identified and documented prior to unblinding.

5.1.1.3 Treatment assignment and treatment groups

If after unblinding it is determined that study participants at any time receive incorrect treatment from their randomized assignment, then for safety and PK/PD analyses these study participants will be reallocated to the appropriate treatment group. For example, if study participants randomized to placebo received rozanolixizumab, then for the safety and PK/PD analyses, these study participants will be reallocated to rozanolixizumab. Study participants randomized to rozanolixizumab will only be reallocated to the placebo treatment group if they never received rozanolixizumab.

Efficacy and safety data will be summarized by randomized treatment group as shown below:

- Placebo
- Rozanolixizumab

5.1.1.4 Center pooling strategy

It is planned to recruit participants in North America, Europe, Australia, and Asia in this study. The data from all sites will be pooled for analyses.

5.1.1.5 Coding dictionaries

Adverse events (AEs) and medical histories will be coded using version 24.1 or later of the Medical Dictionary for Regulatory Activities (MedDRA®).

Medications will be coded according to B3 version Mar 2021 or later of the World Health Organization Drug Dictionary (WHODD).

5.1.1.6 Multicenter studies

Individual center results will not be displayed.

5.1.1.7 Multiple comparisons/multiplicity

A fallback hierarchical testing procedure was planned to be implemented to control the overall type I familywise error rate at 0.05 over the primary endpoint and the 4 defined secondary endpoints. See details in [Section Error! Reference source not found.](#). This however will no longer be implemented due to early study termination and the limited number of study participants.

5.1.1.8 Adjustments for covariates

The efficacy analyses was planned to be adjusted for the following stratification factors (as randomized). This adjustment or any summaries that were planned by these factors, will no longer be possible due to the limited number of participants

- Time from disease onset (≤ 6 months or >6 months from the disease onset),
- Cognitive function (RBANS score of ≤ 85 or >85 at the Screening).

5.1.2 Rescue medication

Rescue medication considered most appropriate for the study participant will be selected by the investigator. The study site will supply rescue medication that will be obtained locally.

Study participants who require rescue medication will discontinue IMP and complete the assessments for the Early Discontinuation Visit.

5.1.3 Missing Data Strategies for efficacy analyses

Table 5-1: Missing data strategies for the analysis of efficacy endpoints

Efficacy endpoint	Statistical analysis category	Statistical Analysis Methods	Imputation Method
Primary	Primary	OR	Any missing daily seizure count in a given reporting period will be (indirectly) imputed with the daily

			average seizure count observed in that period
--	--	--	--

OR: odds ratio

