#### **9.3.1 Primary efficacy analysis**

##### **9.3.1.1 Seizure freedom**

The primary objective of the study is the assessment of the efficacy of rozanolixizumab as measured by seizure freedom. The definition of the primary endpoint together with the description of its primary and supportive analyses are provided in [Table 9-1](#). The main intercurrent event is permanent IMP discontinuation resulting in withdrawal from the randomized Treatment Period, and entering the SFU, or the complete withdrawal from the study (see [Section 7](#)). This will include by design participants who take any rescue anti-seizure medication who will be required to be withdrawn from the randomized treatment. The other intercurrent event is a temporary IMP discontinuation. For the analyses on the RS, participants who withdraw from the study prior to receiving the IMP or who do not have any post-randomization assessment will be considered as not having met the primary endpoint.

For the purpose of deriving the primary efficacy endpoint, any intermittent missing diary seizure count recording will be imputed to non-zero in both treatment arms.

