9.3.1.1 Seizure freedom	
Text added to note that for deriving the primary efficacy endpoint, intermittent missing diary seizure count data will be imputed to non-zero.
	
To clarify how intermittent missing seizure diary days will be handled in the derivation of the primary endpoint.

Section # and Name	Description of Change	Brief Rationale
9.3.2 Secondary efficacy analysis	Text added to define a hierarchical testing procedure for the analysis of the secondary efficacy endpoints.	To control analyses of efficacy-related secondary endpoints for type I error.
9.3.3.2 Seizure reductions	Text updated to note that intermittent missing daily seizure counts in a given reporting period will be (indirectly) imputed with the daily average seizure count observed in that period.	For consistency with changes made to Section 9.3.1.1 relating to imputation of missing seizure count data.
10.6 Appendix 6: Liver Safety – Suggested Actions and Follow-up Assessments	A correction to state that a specific monitoring plan must be agreed for study participants with an ALT of $>3$ ULN (previously $>5$ ULN). Removal of redundant and contradictory text.	Correction and to improve clarity.
10.9.1 China	Section has been removed as the study will no longer be performed in China.	Correction.
10.16 Appendix 16: Management of Infections and Hypogammaglobulinemia	Text has been added to indicate that the unblinded medical monitor will review available safety information for study participants with low IgG levels and may query the site for supportive information. In addition, the unblinded medical monitor may request additional IgG sampling and/or supportive information for any study participants at random to preserve the blind.	To enhance the rigor of the study blind.
10.16: Appendix 16: Management of Infections and Hypogammaglobulinemia	Paragraph 2 updated to be consistent with changes made to criterion #2 in Section 7.1.3.	To add precision to the permanent discontinuation criteria, and to avoid unnecessary withdrawals.

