5.3 Primary Endpoint Analysis

5.3.1 Definition of endpoint

Participants who reported no seizures for 28 consecutive days and maintained the seizure count as zero until the end of Treatment Period will be treated as meeting the primary endpoint.

For the purpose of deriving the primary efficacy endpoint, any intermittent missing diary

seizure count recording will not be imputed but considered as non-zero for the purposes of the primary endpoint.

A by-participant listing of daily seizure count will be provided, including seizure freedom, time to first occurrence of seizure freedom, time to seizure freedom, and duration of seizure freedom.

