5.3.2 Main analytical approach

Participants meeting the primary endpoint will be defined using the strategies indicated below:

Estimand attributes:

1. Treatment conditions:

- Rozanolixizumab: Subcutaneous infusion, [REDACTED]
- Placebo: Subcutaneous infusion, 0.9% sodium chloride aqueous solution (physiological, saline, preservative free).

2. Population of interest: Study participants with LGI1 AIE who comply with the inclusion and exclusion criteria (Protocol Section 5.1 and Section 5.2).

3. Endpoint: Seizure freedom (defined by 28 consecutive days of no seizures) maintained until the end of the Treatment Period (Week 25).

4. Intercurrent events (ICE) / Intercurrent Event Strategy (ICES) and missing data strategies:

- ICE1: Temporary discontinuation from the IMP
- ICE2: Permanent discontinuation from the IMP

The strategies to handle ICEs are summarized below:

Table 5–2: Intercurrent events (ICE) / Intercurrent Event Strategy (ICES) and missing data strategies for the analysis of the primary endpoint

ICE	ICE Strategy	Missing Data Strategy
ICE1	Treatment Policy: The occurrence of intercurrent event ICE1 doesn't affect the assessment of primary endpoint. All seizure counts collected during the treatment period will be included in the assessment of primary endpoint.	See Section 5.1.3 for details.
ICE2	Composite strategy: Permanent discontinuation of the IMP will be considered as non achieving seizure freedom (non-responder).	

5. Population-level summary:

On the RS, odds ratio will be calculated to investigate the association between the treatment and chance to reach primary endpoint.

The ICEs will be handled per [Table 5–2](#).

The data will be summarized in 2×2 contingency table:

Table 5–3: 2 × 2 contingency table

	Rozanolixizumab	Placebo	Row Total
Seizure Freedom	A	B	A + B
No Seizure Freedom	C	D	C + D
Column Total	A + C	B + D	N

Note: A, B, C and D are the number of participants in the cells of the 2×2 table. N represents the total number of participants.

Hypothesis testing

Due to the low number of participants randomized to treatment there will be no hypothesis testing for the efficacy endpoints.

Treatment effect estimation

The OR estimate with its 95% CI will be reported in a summary table using the RS.

The estimate of OR will be computed as (see [Table 5–3](#))

$$\widehat{OR} = \frac{AD}{BC}$$

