and reported to assess the strength and direction of the association with its 95% CI. Resulting $OR > 1$ indicates a clinical benefit from the RLZ, and the magnitude from 1 shows its strength.

In the case where none of the Placebo subjects reaches the primary endpoint, the calculation of the odds ratio estimate is not feasible as it requires division by zero ($B = 0$). In this situation, the OR is not estimable and the median unbiased estimator of the odds ratio (lower end of the 1-sided 50% CI) and 1-sided exact 95% CI will be reported.

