5.5.2 Duration of seizure-free period

The duration of the seizure-free period will be measured from the first day the participant reports no seizures of at least 28 consecutive days until the last day reported without seizures during the Treatment Period. Missing daily seizure counts will be treated as non-zero reports, without any value assigned. This statistic will be provided for each participant.

The endpoint will be included on the listing related to participants seizures; listed on the RS and by randomized treatment arm.

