6.7 Appendix 7: Changes to Protocol-Planned Analyses

Not applicable.

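### SAP Table 5-1 imputes a period average for a missing diary day in the primary endpoint, while SAP 5.3.1 and Protocol 9.3.1.1 count that day as non-zero, so a treatment completer can be a success under one rule and a failure under the other

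*SAP*

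**What the plan says.** The endpoint is 28 consecutive days without seizures, with the count staying at zero to the end of the Treatment Period (SAP 5.3.1). Every one of the last 28 days must therefore be zero. The documents give two rules for a day with no diary entry.

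- **Averaging rule.** SAP 5.1.3, Table 5-1, has one row: primary endpoint, primary analysis, odds ratio. It reads "Any missing daily seizure count in a given reporting period will be (indirectly) imputed with the daily" and continues that the value is the average count observed in the period. The reporting period is not defined.
- **Non-zero rule.** SAP 5.3.1 says that an intermittent missing diary "seizure count recording will not be imputed but considered as non-zero for the purposes of the primary endpoint". Protocol 9.3.1.1 says "any intermittent missing diary seizure count recording will be imputed to non-zero in both treatment arms". SAP 5.5.2 applies the same idea to duration: "Missing daily seizure counts will be treated as non-zero reports, without any value assigned".

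Table 5-1 is live text. Table 5-2 in SAP 5.3.2, which sets out the intercurrent-event and missing-data strategies for the primary estimand, says "See Section 5.1.3 for details" and does not mention 5.3.1. The SAP section headed "6.7 Appendix 7: Changes to Protocol-Planned Analyses" is marked as not applicable, so no departure from the protocol is declared.

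On reporting, SAP 5.3.2 gives the odds ratio with a 95% CI and no test. It adds a special case: "In the case where none of the Placebo subjects reaches the primary endpoint, the calculation of the odds ratio estimate is not feasible". The report then becomes a median unbiased estimate with a one-sided exact 95% interval.

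**The concern.** One rule imputes and the other forbids imputation, for the same variable in the same analysis. A programmer who follows the estimand table applies the average. One who follows the endpoint definition counts the day as non-zero. When the recorded days in the period are all zero, the average is zero and the blank becomes a seizure-free day, so the two programmers classify the same participant differently.

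The odds ratio with its interval is the only efficacy treatment-effect estimate left in the SAP; the secondary endpoints are summarised or listed only. Responder status also organises the PK and PD listings (SAP 5.7.1.1 and 5.7.1.2). With 12 participants, one change of status is visible in the result. If the rule is settled after the data are seen, the choice could be made, or appear to be made, with knowledge of its effect.

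A related inconsistency concerns the data source. SAP 6.1.7.1.1 derives seizure freedom and time to seizure freedom from weekly reported frequency categories, although SAP 5.5.1 describes daily recording and the endpoint counts consecutive days.

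**Working it through.** The plan gives no figure for this point, so there is none to reproduce. The check applies both rules to the same diary and then sizes the consequence.

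**1. The two rules on one diary.** Take a completer whose last 28 days hold 27 recorded zeros and one blank, with no other seizure in the reporting period.

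- Table 5-1: average = 0/27 = 0, the blank becomes 0, all 28 days are zero: success.
- SAP 5.3.1 and Protocol 9.3.1.1: the blank is non-zero: failure.

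If the period average is above zero, both rules give failure.

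**2. Dependence on the undefined period.** Suppose 5 seizures early in treatment, zeros afterwards, and one late blank.

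- Weekly period: 0/6 = 0: success.
- Whole 24 weeks (168 days, 167 recorded): 5/167 = 0.03: failure.

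Table 5-1 therefore does not settle the status by itself.

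**3. Effect on the reported odds ratio.** Inputs are 12 participants (SAP section 3) and planned 1:1 allocation. The 6:6 split and the success counts are assumptions for illustration. One participant is 1/6 = 16.7 percentage points. With OR = AD/(BC) and Wald limits exp(ln OR ± 1.96 × √(1/A + 1/B + 1/C + 1/D)):

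| Rozanolixizumab v placebo | OR | 95% CI |
|---|---|---|
| 4/6 v 2/6 | (4×4)/(2×2) = 4 | 0.36 to 44 |
| 5/6 v 2/6 | (5×4)/(2×1) = 10 | 0.65 to 154 |
| 4/6 v 1/6 | (4×5)/(1×2) = 10 | 0.65 to 154 |

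**4. The zero-cell switch.** For 4/6 v 0/6, condition on 4 successes in 12 and use the noncentral hypergeometric distribution. P(X ≥ 4) = 0.5 at OR 9.64, the median unbiased estimate. P(X ≥ 4) = 0.05 at OR 1.30, the one-sided 95% lower bound. If one placebo participant with a single blank day becomes a success, the table is 4/6 v 1/6 and the report returns to OR 10 (0.65 to 154).

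**5. How often a blank might occur.** Protocol 8.1.1 closes each day's diary after 72 hours and leaves the day blank. The documents give no blank rate. Assuming independent days at rate r, P(at least one blank in 28 days) = 1 − (1 − r)^28:

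| Assumed r | Probability |
|---|---|
| 1% | 24.5% |
| 2% | 43.2% |
| 5% | 76.2% |

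These figures are before any correction when the site reviews the printout and enters the eCRF. Only completers who are otherwise seizure-free in the final 28 days can change status, because permanent discontinuation is a failure under both rules.

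**The case against.** The strongest reply is that two texts written for this endpoint, SAP 5.3.1 and Protocol 9.3.1.1, agree against one table cell. The sample is very small and the SAP itself says power is inadequate. No test is planned, and the intervals are uninformative under either rule. The by-participant listing in 5.3.1 already shows the daily counts. On that view the conflict is an editorial slip. This limits the consequences but leaves the conflict in place, because the estimand table points to the cell that disagrees, and the listing does not say which rule produced the status.

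Several narrower objections have force.

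- **Origin of the row.** The Amendment 3 log in Protocol 10.11 gives nearly the same wording for the former seizure-reductions endpoint: "intermittent missing daily seizure counts in a given reporting period will be (indirectly) imputed with the daily average seizure count observed in that period". That suggests a carried-over row. However, the SAP's own amendment log (6.8.1) records an imputation method being added to 5.1.3 itself. The origin is uncertain and nothing here depends on it.
- **SAP 6.7.** The entry is weak evidence of intent, since the same SAP drops testing, stratified adjustment and multiplicity control without listing them there.
- **Intermittent blanks.** SAP 5.3.1 and Protocol 9.3.1.1 cover intermittent missing days, while Table 5-1 covers any missing day. A run of blanks up to Week 25 has no explicit rule under the former, and the correction must supply one.
- **Zero-cell contrast.** The bound of 1.30 is one-sided, whereas the Wald interval is two-sided. The exact lower limit at 0.025 for 4/6 v 0/6 is 0.91, which includes 1. The apparent change at 1 comes from the switch of interval type set by the SAP, not from the reclassification alone.
- **Blank rates.** They are assumed, and site review may leave far fewer blanks in the eCRF.
- **Categories.** Days recorded only as a non-zero category have no exact average, but only zero versus above zero matters for this endpoint.
- **Weekly source.** The wording in 6.1.7.1.1 might describe how often the form is completed rather than weekly aggregation. It still needs clarifying.

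**Conclusion.** The concern holds. The current SAP gives two incompatible missing-day rules for its primary endpoint, and the primary estimand's table adopts the one that contradicts both SAP 5.3.1 and the protocol. The rules disagree for completers who have at least one blank in the final 28 days, recorded zeros on the other days, and no recorded seizure in whatever period is used for each average. How many of the 12 that describes cannot be known from the documents.

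If it is one participant and the arms are 6:6, that arm's proportion moves by 16.7 points. The odds ratio can change by a factor of 2.5 (4 to 10 in the illustration), or the type of estimate and interval can change if the placebo success count moves to or from zero. The effect is on estimation and reporting, not on a test. It should be fixed because it determines the only efficacy effect estimate that the study will report, and the correction is simple.

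**What to change.** 1. Replace the Table 5-1 row with the rule in SAP 5.3.1 and Protocol 9.3.1.1: a missing day is not imputed and counts as non-zero. State explicitly whether a run of blanks at the end of the Treatment Period is treated in the same way as an intermittent blank.
2. Point the missing-data column of Table 5-2 to 5.3.1.
3. Amend SAP 6.1.7.1.1 so that seizure freedom and time to seizure freedom are derived from the daily records.
4. In the 5.3.1 listing, flag any participant who fails only because of missing days, so that the reader can see how much the rule matters.
5. If the data have already been unblinded, document which rule was applied. The documents do not say whether unblinding has occurred.

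The cost is SAP wording and one listing flag. No new data are needed.
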